Participants:

[figure not shown]
Inclusion Criteria: We will enroll 60 veterans with PTSD. To be eligible for the study, participants must meet current DSM-V diagnostic criteria for PTSD (American Psychiatric Association, 2013). PTSD will be established by interview using the Clinician Administered Posttraumatic Stress Disorder Scale for the DSM-V (CAPS-5; Weathers et al., 2013a). Participants must also indicate current difficulties with anger and aggression as indicated by a score of 20 or higher on the trait anger scale of the State Trait Anger Expression Inventory-2 (STAXI-2, Spielberger, 1999), indicating moderate to severe anger problems. Veterans from all eras will be eligible to participate.

Exclusion Criteria: Participants with a current diagnosis of bipolar disorder, psychotic disorder, or current substance use disorder with severe symptoms. Participants also must not have a seizure disorder and must not be taking any medications that would affect cognition or behavior on the aggression task, including pain medication, benzodiazepines, or antipsychotics. Participants also must not have a positive drug (e.g., amphetamine, opiates, and cocaine) or alcohol urine screen at the post-treatment session (see below), as these substances could affect performance on the study tasks implemented at that session. Finally, participants must not currently be receiving concurrent individual therapy or group therapy focused on anger and aggression and must not currently be participating in the modified TREC group offered at the West Haven VA (WHVA).

Research Design and Methods

For an overview of the time line for study procedures, see Figure 2.

Figure 2. Timeline of Study Procedures

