Trauma Scripting Procedure. After completing the diagnostic interviews (CAPS-5/SCID-5-RV), eligible participants will participate in a trauma-script development procedure as part of a well-validated, script-driven trauma imagery task (Pitman et al., 1987). For this procedure, participants will be asked to identify their most traumatic experience. If they identify more than one event, they will be asked to choose the one that they consider the most distressing. They will first be asked to describe the experience in writing using a script preparation form and then will be asked to indicate which of several different subjective visceral and muscular reactions (e.g., heart beating slower/faster, feeling sweaty, stomach in knots, feeling warm, hands trembling, tension in arms, nausea) may have accompanied the experience. Participants’ written responses will then be reviewed and they will be asked to clarify or expand on the details if necessary. After the session, a script lasting approximately 60 seconds in duration will be composed that portrays the traumatic experience in the second person, present tense, and incorporates the different visceral or muscular reactions. The script will then be audio recorded for playback

during the experimental portion of the post-treatment session. A research assistant (who will be named later upon being hired) will read the narrative scripts to be audio-recorded.

During this baseline session, participants will also complete a battery of self-report questionnaires (see below for full details) to assess baseline levels of anger and aggression.

Randomization Procedures. After participants have completed the Baseline Screening and Evaluation Session they will be randomized to either the TREC group or the MBSR group. To decrease the amount of time participants have to wait before starting group treatment, randomization will be implemented at the group level. That is, after 6 participants are recruited, they will be randomly assigned using urn randomization procedures, to either the TREC group or the MBSR group.

Post-treatment Session: After all participants have completed their assigned interventions (TREC or MBSR) they will be scheduled for the post-treatment session to be held in the biological studies laboratory at the WHVA. At this session, all participants will complete a battery of self-report questionnaires to assess post-treatment levels of anger and aggression (see below).

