| Diagnostic Assessments | | | | | |
| Clinician Administered PTSD Scale for DSM-V: Past-Month Version (CAPS-5) | X | | | | |
| Structured Clinical Interview for DSM-5 Disorders-Research Version (SCID-5-RV) | X | | | | |
| Life Events Checklist-5 (LEC) | X | | | | |
| Primary Outcome Measures: Self-Report | | | | | |
| State Trait Anger Expression Inventory-2 (STAXI-2) | X | X | X | X | X |
| Buss-Perry Aggression Questionnaire (BPAQ) | X | X | X | X | X |
| Primary Outcome Measure: Experimental | | | | | |
| Taylor Reaction Time Task (TRT) | | | | X | |
| Secondary Outcome Measures | | | | | |
| Physiological Reactivity: Heart Rate, Skin Conductance | | | | X | |
| Emotion Regulation: State Difficulties in Emotion Regulation Scale (DERS-S) | | | | X | |
| Exploratory Outcome Measures | | | | | |
| Five Facet Mindfulness Questionnaire (FFMQ) | X | X | X | X | X |
| PTSD Checklist for the DSM-V (PCL-5) | X | X | X | X | X |
| Quantity-Frequency Variability Index (QFI) | X | X | X | X | X |
| Alcohol Dependency Scale (ADS) | X | X | X | X | X |

Baseline Session:

(a) PTSD, other psychiatric disorders, anger and aggression:

The DSM-V criteria for PTSD will be established using the Clinician Administered PTSD Scale: Past-Month Version (CAPS-5, Weathers et al., 2013a). The CAPS-5 will be used to confirm DSM-V PTSD diagnosis and to provide a continuous measure of PTSD severity (CAPS-5 total score). To facilitate the administration of the CAPS, participants will also complete the Life Events Checklist-5 (LEC; Weathers et al., 2013b), which is a self-report questionnaire used to assess the extent to which individuals experienced any of 17 different stressful or difficult life events (e.g., combat exposure, natural disaster, fire or explosion).

Participants will be assessed for psychiatric disorders at the baseline session using the Structured Clinical Interview for DSM-5 Disorders – Research Version (SCID-5-RV, First et al.,

2014). The information from the SCID will be used to exclude participants with severe psychiatric disorders (e.g., schizophrenia or bipolar disorder).

(b) Battery of Self-Report Questionnaires: Participants will also complete a battery of self-report questionnaires including assessments measuring anger and aggression, in addition to trait mindfulness, PTSD, and alcohol use:

- State Trait Anger Expression Inventory-2 (STAXI-2, Spielberger, 1999)
- Buss-Perry Aggression Questionnaire (BPAG; Buss and Perry, 1992)

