- Five Facet Mindfulness Questionnaire (FFMQ; Baer et al., 2008)
- PTSD Checklist for the DSM-V (PCL-5; Weathers et al., 2013)
- Quantity-Frequency Variability Index (QFI; Cahalan, Cisin, & Crossley, 1969)
- Alcohol Dependency Scale (ADS; Skinner & Allen, 1982)

Interim Assessments: During the intervention period, at two time points (weeks 3 and 6 of therapy), participants will be asked to complete the STAXI-2, the BPAG, the FFMQ, the PCL-5, the QFI, and the ADS.

Post-treatment Session: Participants will complete the same battery of self-report questionnaires that was completed at the baseline session. In addition, participants also will complete the following assessments. (See Figure 3 below outlining the order of tasks during experimental portion of the post-treatment session.)

(c) Psychophysiological Assessments: During the experimental portion of the post-treatment session, physiological measurements will be recorded to assess reactivity during exposure to the trauma cue (script). Participants will sit quietly for 5 minutes to collect baseline (B) physiological assessments. This will be followed by the trauma-script reading (TR) and then the trauma-script imagery (TI) segments followed by a resting period (R) and assessment of subjective experiences.

Physiological measurements will include skin conductance levels (SC) and heart rate levels (HR). A BIOPAC MP150 system (BIOPAC, Santa Barbara, CA) that includes modules for HR and SC will be used to record physiologic analog signals. Physiologic analog signals will be digitized by an analog to digital converter. A notebook computer (IBM-compatible) with BIOPAC Acknowledge© software will be used to sample and store the digitized physiologic signals. Interbeat interval will be recorded in milliseconds via standard limb electrocardiogram leads connected to a High Gain Bioamplifier and converted to HR. Skin Conductance (SC) will be measured by an Isolated Skin Conductance coupler using a constant .5 V through 2, 9-mm (sensor diameter) Ag/AgCl electrodes filled with electroconductive gel placed on the hypothenar surface of the subject's non-dominant hand in accordance with published guidelines. The SC electrodes will be separated by 14 mm, as determined by the width of the adhesive collar.

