
[figure not shown]
Electrical stimulation will be implemented using Biopac© equipment. Electrical stimulation will not exceed 100 V for 2 ms duration during the threshold procedure regardless of the participant’s ability to tolerate the shocks. The International Electrotechnical Commission has established recommendations for the amount of electrical stimulation that can be used with human participants (IEC 601-2-10), and the Biopac stimulator STMISOC was engineered so that the available maximum energy output is considerably less than the maximum set by the IEC. The behavior of interest on the TRT is (1) the mean shock level chosen by the participant across all trials, and (2) the number of “20” shocks chosen by the participant.

The validity of the TRT is supported by correlations between behavior on the TRT and self-reported life history of aggressive behavior and trait aggressiveness (Anderson & Bushman, 1997; Giancola & Chermack, 1998; McCloskey & Berman, 2003). The TRT has also been found to be most strongly associated with self-report measures of physical aggression, and to a lesser extent verbal aggression and trait hostility (Giancola & Parrott, 2008). Laboratory aggression paradigms have been the subject of several meta-analyses, including on the effects of various personality traits (Bettencourt et al., 2006) and of exposure to violent media (Anderson & Bushman, 2001) on aggression, and experiments using the TRT have been shown to yield

comparable effects (and effect sizes) to similar field-based studies of aggression (Anderson & Bushman, 1997). Naturally (given the subject matter and use of deception) laboratory aggression paradigms have been subject to close scrutiny (Bertelson, 1990), and the discussion surrounding this methodology has led to modifications of the Taylor task, such as the addition of the “0” shock option, which both enhances the validity of the task by providing a non-aggressive response option and reduces demand characteristics associated with the task (Berman et al., 2009).

(f) Post-TRT Manipulation Check Questionnaire. Participants will complete a post-task questionnaire after completing the TRT to determine the integrity of the experimental aggression manipulation. Participants will be asked to indicate what they thought the purpose of the task was and to indicate characteristics about their “opponent” (e.g., how old they thought their opponent was, whether they were male or female).

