Primary Aim 1 Hypothesis 1.1: Participants assigned to MBSR will report decreased levels of self-reported anger and aggression at post-treatment and at the 3-month follow up compared to those assigned to the TREC group. Scores on the State Trait Anger Expression Inventory-2 and the Buss-Perry Aggression Questionnaire will be used as the primary outcome variables for self-report anger and aggression. Intent-to-treat analyses will be conducted for these outcomes, which will be examined separately. Bonferroni adjustments will be implemented to control for Type 1 error. These data will be analyzed using mixed effects models with treatment, time, and treatment x time interaction as fixed effects. Subject will be the clustering factor and it will be nested within therapy group which will also be considered random. Different variance-covariance structures will be considered and the best one selected based on Schwartz’ Bayesian Information Criterion (BIC). Mixed effects models are the preferred method for analyses of such data as they use all available data on an individual, give unbiased results under general missing data assumptions and provide flexibility in modeling the correlation structure within subject. Significant interactions will be examined further using post-hoc tests.

Primary Aim 1, Hypothesis 1.2: Participants assigned to MBSR will exhibit lower levels of anger and aggression on the TRT compared to those assigned to the TREC group. Mixed effects models will be used to compare the TREC group to the MBSR group on responses on the TRT: (1) mean shock level across the TRT, and (2) total number of “20” shocks chosen on the TRT following the same strategy as for primary aim 1 hypothesis 1.1.

Secondary Aim 1, Hypothesis 1.1: Those assigned to MBSR will exhibit significant decreases in HR and SCL and increases in emotion regulation compared to those assigned to the TREC group. Mixed effects models will be used to compare the TREC group to the MBSR group on physiological variables (HR, SCL) and emotion regulation (DERS-S) following the same strategy as for primary aim 1, hypothesis 1.1.

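### The TRT outcomes are measured once, so for Hypothesis 1.2 the planned mixed model compares only veterans with a usable TRT score and its missing-data rationale does not apply

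*Combined protocol and SAP*

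**What the plan says.** Hypothesis 1.1 (Data Analyses) sets the strategy for STAXI-2 and BPAQ: intent-to-treat; fixed effects for treatment, time and their interaction; subject nested in therapy group, both random. The reason given is that mixed models "use all available data on an individual, give unbiased results under general missing data assumptions".

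Hypothesis 1.2 takes over that strategy for the TRT: "Mixed effects models will be used to compare the TREC group to the MBSR group on responses on the TRT". The two outcomes are "1) the mean shock level chosen by the participant across all trials, and (2) the number of “20” shocks chosen by the participant" (Assessments, (e) Aggression).

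Table 1 has the TRT at post-treatment only: "Taylor Reaction Time Task (TRT) | | | | X". The self-report scales are collected at baseline, post-treatment and follow-up, and also during treatment: "at two time points (weeks 3 and 6 of therapy), participants will be asked to complete the STAXI-2, the BPAG" (Interim Assessments).

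The only other text on missing data is the visual screening that opens Data Analyses. The only covariate committed to every model is medication, yes or no. Other variables enter only if the arms turn out to differ on them, and baseline BPAQ and STAXI-2 are not named.

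**The concern.** A mixed model handles missing values well when a person's other measurements of the same outcome carry information about the missing one. STAXI-2 and BPAQ have up to five measurements per person. The TRT has one, so there is nothing to borrow from and the intent-to-treat intention is not delivered for a declared primary outcome.

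The documents describe several ways a TRT score can be absent or cut short:
- The session is scheduled once the intervention has been completed, with no rule for people who leave treatment (Post-treatment Session).
- The experimenter may stop the task when a participant is too upset, with no scoring rule (In Case of Acute Clinical Distress).
- A participant may decline use of the TRT data after learning of the deception (Debriefing).
- A positive urine screen at that session is an exclusion in Exclusion Criteria but leads to rescheduling in Drug and Alcohol Screening.

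If these routes remove veterans according to their aggression, and do so differently in the two arms, the TRT contrast mixes a treatment effect with a selection effect. HR, SC and DERS-S share the gap, because they too are obtained only at the post-treatment session, and Sample Size and Power Considerations uses them to plan the later trial.

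**Working it through.** **Inputs from the documents.** Sample size: "We will enroll 60 veterans with PTSD". Allocation by therapy group: "after 6 participants are recruited, they will be randomly assigned using urn randomization procedures". That gives 60 / 6 = 10 groups, or 30 veterans per arm if the groups split 5 and 5. There is one TRT occasion. The plan states no attrition rate, TRT standard deviation or effect size, so it has no figure of its own to reproduce here.

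**Step 1: what is left of the model.** Under the Hypothesis 1.1 strategy, for person i in group j at time t:

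Y = β0 + β1·treatment + β2·time + β3·treatment×time + g(j) + s(ij) + e(ijt)

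With one occasion, β2 and β3 do not exist, and the variance of Y is σg² + (σs² + σe²). Only the sum in brackets can be estimated. On simulated data with that sum fixed at 2.2 and the subject part set to 0, 0.5, 1.1 and 2.0, the log-likelihood was −47.03595915 each time. The therapy-group variance remains estimable.

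**Step 2: what a missing score contributes.** A simulated trial of 60 people in 10 groups of 6, with 10 missing outcomes, was fitted by REML with therapy group random. Keeping the 10 incomplete rows or deleting them gave the same estimate (−0.4586), standard error (0.3403) and number analysed (50).

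**Step 3: size of a possible bias.** Assumptions: earlier aggression A is standard normal; TRT has unit SD and correlation r with A; there is no true effect; where absence depends on A, its odds rise by a factor e per SD. Then

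bias = r × (mean A among tested MBSR − mean A among tested TREC).

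With p(a) = 1/(1 + exp(−(c + a))) and c set so that a fraction q is missing, the mean of A among those tested is ∫ a·φ(a)·(1 − p(a)) da / (1 − q). Numerical integration gives −0.091 (q = 10%), −0.133 (15%), −0.173 (20%) and −0.253 (30%). In an arm where absence is unrelated to A, the mean is 0 whatever the rate.

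| Scenario | r = 0.3 | r = 0.5 | r = 0.6 |
|---|---|---|---|
| MBSR only, 20% missing: r × (−0.173) | −0.052 | −0.087 | −0.104 |
| MBSR only, 30% missing: r × (−0.253) | −0.076 | −0.127 | −0.152 |
| Both arms, 30% MBSR and 15% TREC: r × (−0.253 + 0.133) | −0.036 | −0.060 | −0.072 |
| Both arms, 20% each | 0 | 0 | 0 |
| TREC only, 10% missing: r × (+0.091) | +0.027 | +0.046 | +0.055 |
| TREC only, 20% missing: r × (+0.173) | +0.052 | +0.087 | +0.104 |

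Negative values favour MBSR. Simulation with 1,000,000 per arm agrees with the MBSR-only and 30%/15% rows to within about 0.003.

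**Step 4: size relative to noise.** Ignoring clustering, the standard error in SD units is √(1/n1 + 1/n2). With 24 and 27 tested it is √(1/24 + 1/27) = 0.281, and 0.052 / 0.281 = 0.19. With 21 and 24 tested it is √(1/21 + 1/24) = 0.299, and 0.152 / 0.299 = 0.51. The bias is therefore about 0.2 to 0.5 of a standard error.

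**Step 5: what baseline covariates do.** If absence depends only on A and arm, and TRT is linear in A, the regression of TRT on A is the same in tested and untested people. Adjusting for A then removes the bias; simulated fits to tested participants left at most 0.009 SD, which is simulation error. If absence depends on the unseen TRT value, adjustment helps only in part. With 20% missing, r = 0.5, log-odds 0.8 per SD and a true effect of −0.50, dependence in MBSR only gave −0.634 unadjusted and −0.601 using baseline; dependence in both arms gave −0.460 and −0.468.

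**The case against.** The strongest reply is that nothing in the documents shows absence from the TRT to be related to aggression. The cited support is for "correlations between behavior on the TRT and self-reported life history of aggressive behavior and trait aggressiveness", which links the task to aggression, not dropout to aggression. The plan lists retention measures, pays for the session, reschedules after a positive screen and describes dramatic displays during the task as rare. All of this stands. A reader might infer that the angrier veterans will be the ones missing, or that the bias favours MBSR because its sessions last two hours against one for TREC. The documents support neither: they give no attrition rate and no mechanism by arm, and the table shows that the sign can go either way.

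A reader might also infer that the plan claims an unbiased TRT analysis outright. The rationale and the intent-to-treat statement are written for the self-report outcomes and reach the TRT only through the shared strategy. That makes it a claim that does not transfer, rather than an explicit false one.

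Nor does the problem require multiple imputation as the main analysis. With 60 people in 10 groups, imputing by arm alone would ignore the therapy-group effect, and the number of 20-level shocks is a count. Two baseline covariates deal with the case computed in Step 3.

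Finally, this is a pilot, and the later trial's effect sizes are not to be taken from the TRT. That limits the consequence, but the TRT is still a primary outcome, and the same session supplies the HR, SC and emotion-regulation figures that will be used for planning.

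**Conclusion.** The point holds on structure: for Hypothesis 1.2 the planned model is a comparison of randomised veterans with a usable TRT score, clustered by therapy group, and the missing-data argument made for STAXI-2 and BPAQ does not protect it. Whether this biases the result, and in which direction, cannot be settled from the documents.

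Under the assumed rates and correlations, the bias is 0.05–0.15 SD when only MBSR absence depends on aggression, of similar order with the opposite sign when only TREC absence does, and about zero with equal rates and equal dependence. It is modest beside the sampling error of a 60-person trial. The SD figures suit mean shock level; for the count of 20-level shocks they are only a rough guide. It should be corrected because the remedy uses data already collected and costs little.

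**What to change.** 1. In Hypothesis 1.2, prespecify baseline BPAQ and STAXI-2 trait anger as covariates whether or not the arms differ. Drop the time terms and the subject random effect, and keep the therapy-group random effect. Use the same covariates for HR, SC and DERS-S. If repeated readings within that session are modelled (DERS-S is taken twice), a within-session term may stay, but it does nothing for someone who missed the session.
2. Limit the sentence on using all available data and being unbiased to STAXI-2 and BPAQ, and state that Hypothesis 1.2 analyses randomised participants with a usable TRT score.
3. Optionally, as a sensitivity analysis only, use a short imputation model that respects therapy group and the count outcome and adds the week-3 and week-6 BPAQ and STAXI-2 scores, with a shift for values missing not at random. Leave out anyone who declined use of their TRT data.
4. Reconcile Exclusion Criteria with Drug and Alcohol Screening on a positive screen at the post-treatment session.

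Cost: SAP wording, two covariates in a 60-person model, and slightly more analysis work. No new data are needed.

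### Adjustment of the two TRT primary outcomes for baseline aggression (BPAQ) is not pre-specified and is left to a data-dependent imbalance check, which gives up most of the available precision

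*Combined protocol and SAP*

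**What the plan says.** Table 1 schedules the TRT at the post-treatment visit only ("Taylor Reaction Time Task (TRT) | | | | X") and the BPAQ at all five assessments, baseline included ("Buss-Perry Aggression Questionnaire (BPAQ) | X | X | X | X | X"). Under Randomization Procedures, allocation follows the baseline session, so baseline BPAQ precedes randomisation.

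Data Analyses, Primary Aim 1, Hypothesis 1.2 compares the arms on mean shock level and on the number of '20' shocks "chosen on the TRT following the same strategy as for primary aim 1 hypothesis 1.1". The Hypothesis 1.1 strategy is "mixed effects models with treatment, time, and treatment x time interaction as fixed effects", with subject nested in a random therapy group and a Bonferroni adjustment. No baseline aggression score is named.

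The opening paragraphs of Data Analyses add two things. Medication use (yes/no) is in every model. The arms are also compared on demographic variables and on an expressly open list of others, with psychiatric symptoms and trait mindfulness as examples; any variable that differs becomes a covariate. BPAQ is neither named nor excluded, and no test or threshold is given.

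On prognostic value, the Aggression section under Assessments says: "The TRT has also been found to be most strongly associated with self-report measures of physical aggression". It gives no correlation.

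**The concern.** In Hypothesis 1.1 a participant's starting level enters through the time factor. With one TRT score per person, time and its interaction drop out. That leaves treatment, medication and the therapy-group effect. Stable differences in aggressiveness between people then stay in the error term, although the plan holds a pre-treatment measure that it regards as related to the outcome.

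Allocation makes this more than a detail. The plan says "randomization will be implemented at the group level", in sets of six, so only about ten units are randomised and moderate chance differences in baseline aggression are likely. The TRT is the only primary outcome that is not self-reported. Whether its model contains baseline aggression would be decided after looking at the data, by a rule that two analysts could apply differently.

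**Working it through.** **Inputs from the documents.** Sample size: "We will enroll 60 veterans with PTSD" (Inclusion Criteria). Unit: "after 6 participants are recruited, they will be randomly assigned using urn randomization procedures, to either the TREC group or the MBSR group" (Randomization Procedures). Hence 60/6 = 10 groups and, with two arms, 10 − 2 = 8 df at group level. The plan derives no power figure, so there is none to reproduce.

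**Assumptions.** Equal arms (30 each); BPAQ-TRT correlation r from 0.1 to 0.5; ICC 0 or 0.05; two-sided alpha 0.05, with 0.025 as a Bonferroni variant; p<0.05 as the imbalance trigger; a continuous outcome.

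**Chance imbalance in BPAQ.** At ICC 0 the SE of the baseline arm difference is sqrt(2/30) = 0.258 SD. The chance of a difference above +0.3 SD in a given direction is P(Z > 0.3/0.258) = 12%, or about 25% counting both directions. A t-test on 58 df reaches p<0.05 only beyond about 2.00 × 0.258 = 0.52 SD, so differences from 0.3 to 0.5 SD normally go unadjusted.

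**What such an imbalance does (r = 0.4, ICC 0, no true effect).** Given an imbalance above +0.3 SD, its mean is about 0.43 SD, and 0.4 × 0.43 = 0.17 SD passes into the unadjusted TRT difference. In simulation the trigger fired in about 20% of these trials. The mean spurious TRT difference was 0.17 SD unadjusted, 0.12 SD under test-then-adjust and about 0 if always adjusted.

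**Precision.** Simulated variance of the arm difference relative to no adjustment (20,000 trials per row, 10 groups of 6, ICC 0):

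| r | always adjust | test-then-adjust |
|---|---|---|
| 0.1 | 1.01 | 1.00 |
| 0.2 | 0.97 | 0.99 |
| 0.3 | 0.92 | 0.98 |
| 0.4 | 0.86 | 0.96 |
| 0.5 | 0.76 | 0.93 |

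At r = 0.4 the unrounded ratios are 0.856 and 0.959, so the conditional rule recovers 0.041/0.144 = 28% of the gain. At ICC 0.05 the corresponding ratios are 0.88 and 0.97.

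**Power.** An individual-level covariate does not remove variance created by sharing a therapy group, so only the individual part is reduced: Var = (2/30)(1 + 5·ICC − r²). Noncentral t, 8 df, difference 0.7 SD, ICC 0.05, alpha 0.05:

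| r | SE | power |
|---|---|---|
| 0 | 0.289 | 56.8% |
| 0.1 | 0.288 | 57.1% |
| 0.2 | 0.284 | 58.1% |
| 0.3 | 0.278 | 59.9% |
| 0.4 | 0.270 | 62.5% |
| 0.5 | 0.258 | 66.2% |

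The gain at r = 0.4 is 62.5 − 56.8 = 5.7 points. For a 0.5 SD difference it is 37.2 − 33.3 = 3.9 points, and 3.2 points at alpha 0.025 (from a base of 22%). At 0.7 SD the smaller alpha mainly lowers the base: 42.4% to 48.0%, 5.6 points.

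**The case against.** - **The plan is not silent on covariates.** A reader might infer that the TRT arms are compared with no adjustment, or that BPAQ is shut out. The documents do not support that: medication is always included, and the open list could admit BPAQ if it differed. This stands, and it narrows the point to conditional versus fixed adjustment.
- **There is no bias.** A reader might take the 0.17 SD shift as bias in the planned estimate. Over randomisations the unadjusted comparison is unbiased. The shift is conditional on an imbalance that occurs in about 12% of trials in a given direction. This stands.
- **The correlation is unknown and could be low.** Entry requires a trait anger score of 20 or more, which may restrict the range of aggression. An eight-week intervention separates baseline BPAQ from the TRT. The plan reports a weaker TRT link with verbal aggression and hostility than with physical aggression, so a total score may correlate less well. This stands, and is why low values are shown.
- **Larger power gains are easy to obtain.** Multiplying the whole variance by 1 − r² gives 60.7%, 64.1% and 69.0% at r = 0.3, 0.4 and 0.5, but that wrongly shrinks the therapy-group variance too.
- **This is a pilot.** Sample Size and Power Considerations says significance may not be reached, and the effect sizes it lists for planning the next trial do not include the TRT. That limits the consequence. It does not justify an unspecified covariate rule for a primary outcome, since the same section looks to a pattern of promising results.

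**Conclusion.** The point holds as one about pre-specification and efficiency. The TRT models do not fix adjustment for baseline aggression, and the rule that could bring it in is undefined and data-dependent. If that rule means a test at p<0.05, it forgoes roughly 70% or more of the attainable variance reduction at correlations of 0.3 to 0.5. It also leaves most moderate imbalances uncorrected.

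The benefit of fixed adjustment is modest: about 3 to 9 power points for a 0.7 SD difference at those correlations (ICC 0.05, alpha 0.05). It is less for 0.5 SD, and close to nil at 0.2 or below. These figures rest on assumed correlations, effect sizes, ICC, equal arms and full follow-up. They apply to mean shock level; the gain for the count of '20' shocks has not been quantified. The change is worth making because it costs almost nothing, not because the planned comparison is invalid.

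**What to change.** In Data Analyses, Primary Aim 1, Hypothesis 1.2, state that both TRT models (mean shock level and number of '20' shocks) include each participant's baseline BPAQ total as a fixed continuous covariate, whether or not the arms differ on it, and keep the therapy-group random effect. Use the baseline value only, since treatment can change the week 3, week 6 and post-treatment scores.

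Enter the score at the individual level. Adjusting ten group means on 8 df would change the confidence interval width by a factor of 1.06 at r = 0.3 and 0.96 at r = 0.5, so it could do harm.

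The cost is one sentence and one individual-level degree of freedom, with no new data. If the correlation is near zero the loss is negligible (about 1% of variance at r = 0.1 in the simulation).
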